7.4 Safety assessments

There will be assessments of risks and anticipated adverse device effects which are described in section 18.

7.5 Further data of interest

Additional information will be collected to characterize the study population and safety and efficacy of the investigational devices. The data will be statistically analyzed, where appropriate (see section 11). Specifically, further data of interest will include:

- Demographics including age, gender, weight and height
- Medical history
- Indication for device therapy
- Assessment of insertion procedure and insertion tool performance
- Assessment of device programming
- Assessment of P-wave visibility

8 DESIGN OF THE CLINICAL INVESTIGATION

8.1 General considerations

8.1.1 Type of clinical investigation

This is an open, prospective, single-arm, multi-site, non-randomized, explorative study, which will be conducted at Australian sites.

8.1.2 Measures taken to minimize or avoid bias

The study is conducted according to BIOTRONIK CCR Standard Operating Procedures which describe in detail measures and actions to minimize bias.

To avoid undue influence of single investigators of the evaluation of the insertion procedure, a high number of investigators (up to 15) shall take part in the insertions and contribute to a comprehensive assessment of the new insertion procedure. The maximum insertions per investigator are limited to 5. Exemptions will be communicated in written form in case enrollment is too slow.

8.1.3 Selection of measurements for endpoints

No statistical endpoints are defined.

8.1.4 Methods

8.1.4.1 eCRFs

During the course of the study, all clinical procedures are performed according to clinical routine. All parameters and measurements that are recorded within the study are described in this section and will be documented on eCRFs. The corresponding time schedule is given in section 9:

- Enrollment / Baseline visit
- Insertion visit, incl. assessment of insertion procedure
- 1-week follow-up visit
- 1-month Home Monitoring observation and telephone interview
- Adverse Event form
- Device Deficiency form
- Study termination form

All data have to be available for source data verification during monitoring visits of the sponsor. Patients have to consent to the use of their medical data in the patient file prior to enrollment by signing the informed consent form. Information given on source data sheets, e.g. for documenting insertion procedure assessment (insertion visit) and the patient telephone interview (1-month Home Monitoring observation) is accepted as source data.

8.1.4.2 Source data verification of enrollment criteria

For the following inclusion/exclusion criteria, the eCRF is accepted as source:

- Patient is able to understand the nature of study and has provided written informed consent.
- Patient is willing and able to perform all follow up visits at the study site.
- Patient is not pregnant or breast feeding.

- Patient is not participating in another interventional clinical investigation
- Patient's life-expectancy is not less than 6 months.

8.1.4.3 Patient demographics and medical history

After obtaining informed consent, the following information has to be entered in the baseline eCRF:

- Date of Enrollment / Baseline visit
- Demographic characteristics (age, gender, height, weight)
- Details on the ICM-indication of the patient
- Medical history of patient, medication

8.1.4.4 Insertion

After the insertion procedure the following information has to be entered in the respective eCRF:

- Date of insertion
- Serial number of BIOMONITOR III, CardioMessenger and Remote Assistant III
- Position and orientation of the BIOMONITOR III device
- Information on the insertion, handling of tools, including start time and end time of insertion procedure
- R-wave measurements (based on programmer screen)
- Device interrogation and provision of programmer download
- Adverse Event information
- Device Deficiency information

8.1.4.5 1-week follow-up

At the 1-week follow-up visit the following information has to be entered in the respective eCRF or provided via HMSC:

- Date of visit
- R-wave measurements (via HMSC)
- Noise rate measurements (via HMSC)
- P-wave visibility assessments
- Changes in device programming, if appropriate
- Device interrogation and provision of programmer download
- Adverse Event information
- Device Deficiency information

8.1.4.6 1-month Home Monitoring observation and telephone interview

The investigator is asked to consult the Home Monitoring Service Center (HMSC) one month after insertion and evaluate technical and diagnostic data. Additionally a telephone interview with the patient shall be conducted. The following information has to be entered in the respective eCRF or provided via HMSC:

- Dates of evaluated daily transmissions with periodic sECGs
- R-wave measurements (via HMSC)

- Noise rate measurements (via HMSC)
- P-wave visibility assessment
- Changes in device programming, if appropriate
- Answers given by the patient during the telephone interview
- Adverse Event information (based on a telephone interview with the patient)
- Device Deficiency information (based on a telephone interview with the patient)

8.1.4.7 Adverse Events and Device Deficiencies

The investigator has to record any adverse event or device deficiency which occurs during study duration on the corresponding eCRF. The adverse event will be classified according to the seriousness, the relation to the investigational devices and to the procedure. The definition of event classification is described in section 18.

8.1.5 Equipment to be used for the assessment of variables

The following equipment is used during the study to collect data in combination with the BIOMONITOR III devices or as accessory:

- External programming device: BIOTRONIK Renamic or successors
- BIOTRONIK programmer software: Current and subsequent versions
- Remote monitoring tools: BIOTRONIK Smart 3G (or successors)
- Remote monitoring software: HMSC 3 or successors

All devices are used within their intended purpose.

8.1.6 Replacement of subjects

Patients who drop-out before insertion will be replaced. Therefore it is possible that more than 45 patients are enrolled in order to get data from 45 insertions.

8.2 **Used devices and comparators**

8.2.1 Description of exposure to the investigational device and/or comparator

No comparator is used in this study.

8.2.2 Justification of the choice of comparators

No comparator is used in this study.

8.2.3 List of any other medical device and/or medication to be used during the investigation

- During conduct of the insertion procedure, local anesthesia will be applied around the incision and location of the device pocket.
- Additionally, local and systemic antibiotics might be applied to the patient to prevent wound infection prior and / or after the insertion procedure, according to local clinical practice.

8.2.4 Number of investigational devices to be used and a justification

In this clinical investigation a maximum of 45 individuals will be enrolled (plus potential replacements for drop-outs prior to insertion). To ensure device availability in up to 15 study sites and to account for possible device replacements, about 50 BIOMONITOR III systems will be provided.

For device interrogation up to 15 study sites will be supplied with a Renamic programmer device each, running the study specific programmer software.

8.3 Subjects

8.3.1 Description of patient population

The patient population consists of patients in whom long-term cardiac rhythm monitoring may be required for diagnostic purposes. Indications are described in sections 4.1.3 and 4.6.1.

8.3.2 Inclusion criteria

To be eligible for participation in the BIO|CONCEPT.BIOMONITOR III study, patients must fulfill at least one of the following four inclusion criteria:

- Patient is at high risk of developing a clinically important cardiac arrhythmia; **or**
Patient is undergoing investigation for symptoms such as palpitations, pre-syncope or syncope, that are suggestive of an underlying cardiac arrhythmia; **or**
Patient is undergoing investigation for the detection of atrial fibrillation following cryptogenic stroke; **or**
Patient is planned for AF ablative procedure or has already undergone an AF ablative procedure.

Additionally, the following inclusion criteria must be fulfilled:

- Patient is able to understand the nature of study and has provided written informed consent.
- Patient is willing and able to perform all follow up visits at the study site.
- Patient is willing and able to use the CardioMessenger and accepts the BIOTRONIK Home Monitoring concept.

8.3.3 Exclusion criteria

- Patients implanted with ICD or pacemaker.
- Patient is pregnant or breast feeding.
- Patient is less than 18 years old.
- Patient is participating in another interventional clinical investigation according to the definition given below.^{1,2}
- Patient's life-expectancy is less than 6 months.

¹Based on the EU Clinical Trials Regulation a study is considered as interventional which fulfils any of the following conditions: (a) the assignment of the subject to a particular therapeutic strategy is decided in advance and does not fall within normal clinical practice of the Member State concerned; (b) the decision to prescribe the investigational medicinal products is taken together with the decision to include the subject in the clinical study; or (c) diagnostic or monitoring procedures in addition to normal clinical practice are applied to the subjects.

²Patients shall not be enrolled in two interventional clinical investigations at the same time. Enrollment of patients who are already enrolled into an interventional clinical investigation is prohibited by an exclusion criterion. If the patient wants to consent for another study, and the investigator knows this beforehand, the investigator shall ask for an agreement from the sponsor, and if not granted, shall ask the patient not to participate in the second study. If the investigator finds out that the patient has been enrolled into another study, the investigator shall inform the sponsor (see section 9.10.2 "Responsibilities of the investigator"). The sponsor may decide to exclude the patient from the study only if further CIP required procedures offer a risk of a reciprocal effect with the treatment of the other study.

Decisions and deviations have to be discussed upfront (if applicable, during the advisory stakeholder meeting) and documented respectively (e.g. via Note to File and reported as CIP deviation or supporting document "Internal Steering Committee").

8.3.4 Drop-out criteria

8.3.4.1 Exclusion by investigator decision

Since no invasive, stressful or risky procedures are planned by this protocol after the insertion, it is not allowed that a patient is excluded from the study by decision of the investigator once an insertion has been attempted. This does not infringe on the investigators' right, and obligation, to refrain from any study procedure that may not be medically justified. It is merely intended to assure complete reporting of adverse events from the complete study duration.

8.3.4.2 Exclusion after failed insertion or explantation

Patients in whom the insertion fails or in whom the study device is explanted shall be excluded after all adverse events are terminated and the corresponding eCRFs have been thoroughly completed.

8.3.4.3 Withdrawal of patient consent

Patients may withdraw their consent for study participation at any time without stating a reason and without any unfavorable consequences. In any case, no further collection of data will occur. If the patient chooses to withdraw consent concerning both, study participation as well as the processing of personal data he/she will no longer take part in the study and the data will be anonymized or deleted, so that it is impossible to reconnect the data to the patient's identity.

In case the patient chooses to leave the consent for the processing of personal data unaffected, BIOTRONIK will further store, process and analyze the pseudonymized data that was collected prior to withdrawal.

8.3.5 Point of enrollment and study termination

Date of enrollment is the date of signature of the informed consent form.

Date of termination is either the date of the 1-month telephone interview, or – e.g. when no interview was possible - the date of the CardioReport, which is basis for the 1-month Home observation data (see 8.1.4.6).

8.3.6 Timelines

First patient in (FPI): ~ Feb 2019

Last patient in (LPI): ~ May 2019

Enrollment period: ~ 3 months

Last patient out (LPO): ~ Jun 2019

Duration of study participation: ~ 1 month

Finalization of study report ~ Sep 2019

The end of the clinical study is defined as the date of termination of the last patient (last patient out).

9 STUDY PROCEDURES

9.1 Overview

Subsequent to the enrollment and the insertion of the investigational device, one follow-up visit and a Home Monitoring observation one month after the insertion are scheduled. During all study visits designated BIOTRONIK employees who are appropriately trained on the subject matter are allowed to handle programmer data.

The visits and observations should take place within a certain time frame as listed in **Table 2**. This schedule should be followed as closely as possible. If circumstances prevent the presence of the patient at the follow-up visit, the reason for the missed follow-up has to be indicated on the respective eCRF.

Table 2: Overview of study procedures

	Enrollment / baseline	Insertion	1-week follow-up -2 days / +1 week	1-month Home Monitoring observation, telephone interview
Check inclusion / exclusion criteria	X			
Obtain informed consent	X			
Demographics, medical history, indication	X			
Insertion of BM III and assessment of insertion procedure and tool handling		X		
Interrogate BM III device and provide programmer data		X	X	
Program BM III with indication specific settings		X		
Program periodic subcutaneous ECG (cycle duration 1 day)		X		
Provide CardioMessenger and Remote Assistant, incl. test of Remote Assistant		X		
R-wave amplitude (based on programmer screen)		X		
R-wave amplitude (via HMSC)			X	X
Noise rate (via HMSC)			X	X
Assess P-wave visibility, based on periodic sECGs			X	X
Read-out of BM III data (RAM-dump)			X	
Restart statistics and recordings after read-out of BM III data			X	
Patient interview via telephone				X
Adverse Event and Device Deficiency reporting	X	X	X	X
Fill-in eCRFs	X	X	X	X

9.2 Enrollment / Baseline

Prior to enrollment into the clinical investigation, the investigator will evaluate the eligibility of each patient considering all inclusion and exclusion criteria (see sections 8.3.2 and 8.3.3). The informed consent must be obtained before initiating any study related procedures. The consent process, including discussion of the study related aspects, will be documented in the subject's medical record. After obtaining informed consent, the subject has to be registered in the iMedNet System. After registration, the patient will be assigned a pseudonymized ID code to be used in the study and the patient has to be entered in the patient identification log.

In the enrollment eCRF the following data has to be recorded:

- Version number of the ICF
- Confirmation that patient met all inclusion and none of the exclusion criteria
- Confirmation that the patient dated and signed the patient ICF personally
- Date of patient signature on the informed consent form
- Date of investigator signature on the informed consent form

After a subject has been enrolled, the following data should be collected and entered in the baseline evaluation eCRF.

- Date of enrollment / baseline visit
- Demographic characteristics (date of birth, gender, height, weight)
- Details on the ICM indication of the patient
- Medical history of patient

9.3 Insertion visit

The device insertion should be completed within 4 week after informed consent. Otherwise the patients study participation will be terminated.

9.3.1 Device insertion

BIOMONITOR III should be inserted as described in the IFU and in accordance with section 4.7.1.10. The investigator determines the insertion site in accordance with the individual patient characteristics. Time of insertion start and time of final wound closure should be documented on the insertion source data sheet (SDS) (see section 9.3.2).

If the patient consents to a video recording as described in the consent form, the implantation procedure itself is allowed to be videotaped. The patient's face shall not be identifiable in that recording. Recording of the insertion should not delay the insertion procedure or otherwise interfere with the clinical routine.

9.3.2 Procedure after insertion

The following procedures shall be conducted after insertion:

- Interrogate the newly inserted BIOMONITOR III device.
- Freeze, store and print the sECG window and document the R-wave amplitude value on the insertion SDS. In case of varying amplitude labeling, document both, the lowest and the highest amplitude value (Figure 9 and Figure 10).

[figure not shown]

Figure 9: Freeze screen during interrogation

[figure not shown]

Figure 10: Document R-wave amplitude based on programmer screen or printout

- Program the BIOMONITOR III according to the clinical indication of the patient. Consider using the indication specific program settings (Go to 'Parameters' - 'Program sets' - 'Program consult', Figure 11)

[figure not shown]

Figure 11: Use 'ProgramConsult' for indication specific programming

- Program the Home Monitoring function to 'ON'

- Store the electronic procedure data (including final device settings, measurements) of the BIOTRONIK programmer. Provide the programmer data by uploading the PDF-File to the EDC-database (iMedNet) or by using the ReportShare-function (see 4.7.1.11). Alternatively, the PDF file can be send to the study e-mail address ([contact]).
- Register the patient at the Home Monitoring Service Center (HMSC).
- Activate a periodic sECG recording in the `Patient profile` tab of the HMSC (Go to `Remote scheduling`, press `edit` and select `daily`), Figure 12.

Configuration	
Remote Scheduling	 disabled  periodic  daily
Next HM follow-up	November 01 2018
Days between two HM follow-ups	91
HM follow-ups shall occur on	any day

Figure 12: Activate daily periodic sECG recording in HMSC

- Provide the Remote Assistant III to the patient and explain how to use the Remote Assistant III correctly. Let the patient trigger one sECG recording.
- Complete the insertion SDS and enter data in the insertion eCRFs in the iMedNet EDC database.
- Document any adverse event or device deficiency during the procedure by using the respective eCRF. Adhere to the reporting timelines listed in section 18.

9.3.3 Assessment of the insertion procedure

The investigator needs to give details on the insertion procedure and should assess the insertion procedure and tool handling. The following data shall be provided on the insertion SDS and eCRF:

- Time of insertion start
- Time from incision to insertion end
- Time from incision to wound closure
- Insertion site and BIOMONITOR III orientation
- Type of pocket closure
- Usage of anesthesia and antibiotics
- Device repositioning, if applicable
- Assessment of incision tool handling
- Assessment of FIT OneStep insertion tool handling

9.4 1-week follow - up

After 1 week (-2 days / +1 week) following the device insertion, patients return to the investigation site for an in-office assessment of their implanted system. The following procedures shall be conducted:

- Interrogate the BIOMONITOR III device.
- Adjust patient specific program parameters, if applicable. Consider using the indication specific program settings (Go to `Parameters` – `Program sets` – `Program consult`).
- Store the electronic procedure data (including final device settings, measurements) of the BIOTRONIK programmer. Provide the programmer data by uploading the PDF-File to the EDC-database (iMedNet) or by using the ReportShare-function. Alternatively, the PDF file can be send to the study e-mail address ([contact]).
- Perform a complete device data read out (i.e. RAM –dump, see 9.7).
- Restart device statistics
- Within the HMSC:

Inspect the first periodic sECG episode after the day of insertion. In patients with sinus rhythm, evaluate the number of expected and observed P-waves which can be undoubtedly identified.

Inspect the latest periodic sECG episode which was successfully transmitted to the HMSC. In patients with sinus rhythm, evaluate the number of expected and observed P-waves which can undoubtedly be identified.
- Enter the dates and values in the 1-week follow up SDS. Provide a PDF file export (CardioReport) from the HMSC with the respective episodes and upload the PDF-Files to the EDC-database (iMedNet). Alternatively, the PDF files can be send to the study e-mail address ([contact]).
- Inspect the trend values for sensing amplitude (R-wave amplitude) and noise burden. Values are automatically provided via HMSC, therefore no eCRF entry is necessary.
- Complete the 1-week follow up SDS and enter data in the 1-week eCRFs in the iMedNet EDC database.
- Document any adverse event or device deficiency observed during the follow-up by using the respective eCRF. Adhere to the reporting timelines listed in section 18.

9.5 1-month Home Monitoring observation and telephone interview

One month after the device insertion, the investigator is asked to enter the HMSC and to inspect the daily transmissions of the patient. Additionally, the patient should be contacted via telephone and shall be interviewed. The following procedure shall be conducted:

- Within the HMSC:

Inspect the periodic sECG episode, which is closest to 30 days after insertion date and which was successfully transmitted to the HMSC. In patients with sinus rhythm, evaluate the number of expected and observed P-waves which can undoubtedly be identified.
- Enter the date and values in the 1-month follow up SDS. Provide a file export (CardioReport) from the HMSC with the respective episode and upload the PDF-File to the EDC-database (iMedNet). Alternatively, the PDF file can be send to the study e-mail address ([contact]).

- Inspect the trend values for sensing amplitude (R-wave amplitude) and noise burden. Values are automatically provided via HMSC, therefore no eCRF entry is necessary.
- Contact the patient via a telephone call and question the patient about any adverse events related to the BIOMONITOR III or the insertion procedure. Ask the patient to answer the questions given on the 1-month follow-up SDS regarding the wearing comfort of the BIOMONITOR III and usability of the Patient APP, if applicable.
- Document any adverse event or device deficiency by using the respective eCRF. Adhere to the reporting timelines listed in section 18.
- Complete the 1-month follow up SDS and enter data in the 1-month eCRFs in the iMedNet EDC database.

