9.8 Termination and post treatment

The study termination eCRF must be completed to determine the end and reason for study termination of the individual patient. The regular termination of the patient is defined as the time when the 1-month Home Monitoring observation and telephone interview is completed. The frequency and elements of routine visits according to standard guidelines for ICM therapy are adequate for all patients after regular study termination.

In the case of patients who do not show up for the scheduled 1-week follow-up, all efforts should be made to contact them and complete the required checks, even if this would be far out of the planned schedule. Equally, all efforts should be made to contact the patient for the 1-month follow-up to assure that no adverse events will remain unnoticed. It should be kept in mind that the study device has no market approval and is implanted only under the condition that the patient is followed in this study.

Follow-up of subjects which have withdrawn consent is covered in section 8.3.5.1.

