18.1 Definition of adverse events

An AE is defined* as any untoward medical occurrence, unintended disease or injury, or untoward clinical signs (including abnormal laboratory findings) in subjects, users or other persons whether or not related to the investigational device. This includes:

- Events related to the investigational device or the comparator
- Events related to the procedures involved
- For users or other persons, this definition is restricted to events related to the investigational devices.

*see ISO 14155 3.2

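### The 1-month call asks only about device- or procedure-related events, and patients with failed insertion or explantation have no minimum adverse event follow-up, so late events may be under-elicited

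*Protocol*

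**What the plan says.** **What is to be recorded.** Section 8.1.4.7 states: "The investigator has to record any adverse event or device deficiency which occurs during study duration on the corresponding eCRF". Section 18.1 defines an adverse event as an untoward occurrence "in subjects, users or other persons whether or not related to the investigational device". Section 8.1.4.6 takes the 1-month adverse event information from the telephone interview and sets no relatedness limit. Section 18.2.1 has the investigator grade causality on five levels, with sponsor review. The synopsis lists adverse events and adverse device effects as separate items.

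**What the patient is asked.** The instruction for the 1-month call in section 9.5 is: "Contact the patient via a telephone call and question the patient about any adverse events related to the BIOMONITOR III or the insertion procedure". The next bullet of the same section says: "Document any adverse event or device deficiency by using the respective eCRF".

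**Who stays under observation.** Section 8.3.4.1 bars the investigator from excluding a patient once insertion has been attempted, and explains: "It is merely intended to assure complete reporting of adverse events from the complete study duration". Section 8.3.4.2 then says: "Patients in whom the insertion fails or in whom the study device is explanted shall be excluded after all adverse events are terminated", once the eCRFs are also complete. It gives no minimum time. Section 5.3 treats 4 weeks as a sufficient period of safety follow-up.

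**The concern.** The question is narrower than the data it has to supply. The patient is asked to decide what is related before the investigator hears of the event, although the protocol gives that decision to the investigator. The events most exposed are non-serious ones that a patient would not connect with a small chest implant. Table 3 in section 18.7 lists several of these among the anticipated effects of insertion with unknown frequency: presyncope, dyspnea, supraventricular tachycardia and pain away from the insertion site. The inclusion criteria admit patients under investigation for palpitations, pre-syncope and syncope. Such a patient could reasonably put a new episode down to the existing complaint and answer no.

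The exit rule raises a related problem. A patient whose insertion failed, or whose device was removed, and who has no open event can leave before one month. A wound problem that appears afterwards has no route into the data, and these are patients whose procedure or device course went badly.

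This is a first-in-man study. Section 11.2 justifies its size by the chance of seeing unforeseen risks before market introduction, and section 11.6 uses all available data for the launch decision. An event that was never elicited cannot be recovered at analysis.

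**Working it through.** **1. Contacts after insertion (Table 2, sections 9.4 and 9.5).** The 1-week visit has a window of -2 days to +1 week, so it falls on day 5 to 14. The next scheduled contact with the patient is the call at about day 30. The call is therefore the only planned enquiry covering roughly the last 30 - 14 = 16 to 30 - 5 = 25 days. Unscheduled visits (9.6) and the continuous reporting duty (18.9) add to this, but the duty in 18.9 is framed around serious events and serious device deficiencies.

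**2. Question against recording rule.**
- Record: any event (8.1.4.7, 18.1, and the documentation bullet in 9.5).
- Judge relatedness: the investigator (18.2.1).
- Ask at the call: related events only (9.5).

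The first two agree with each other. The third does not fit them, because a site can document only what it learns.

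**3. Exit rule against its stated aim.**
- 8.3.4.1: events are to be reported from the complete study duration.
- 5.3: 4 weeks of safety follow-up.
- 8.3.4.2: exit when existing events have ended, which for a patient without an open event can be straight away.

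What is lost is limited to events that begin after exit.

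**4. How many patients the exit rule touches.** In the BioMonitor 2 Master Study (5.2.2), 92 patients were enrolled and one withdrew before insertion, leaving 91 attempts with 1 failure. Applied to this study: 45 × 1/91 = 0.49, about 0.5 patients. That study also had 2 explantations, but over 3 months. Adding them gives 45 × 3/91 = 1.48, which is too high as a 1-month figure. In the BioMonitor 2 pilot study all insertions succeeded.

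**5. Can the effect of the question be sized?** Only under an assumption. Section 11.2 states that 45 patients give 95% confidence of at least one event of a type occurring with 15% probability. Computed directly, 1 - (1 - 0.15)^45 = 99.93%. The statement therefore holds as a lower bound but is not sharp: ln(0.05)/ln(0.85) = 18.4, so 19 patients would be enough. Let s be the share of such events that is captured. The documents give no value for s. With 1 - (1 - 0.15s)^45:

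| s (assumed) | Chance of at least one recorded event |
|---|---|
| 1.0 | 99.9% |
| 0.8 | 99.7% |
| 0.5 | 97.0% |
| 0.3 | 87.4% |

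The chance stays at or above 95% until s falls below about 0.43, from (1 - 0.05^(1/45))/0.15 = 0.0644/0.15. Using one s for the whole month is itself pessimistic, since the insertion and 1-week contacts carry no such filter.

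**The case against.** The strongest reply is that the protocol requires every event to be documented, and says so in the same section as the restricted question. Events are also collected at insertion, at the in-office 1-week visit and at interim visits. Section 18.9 treats the site's own medical records as known to the study team. Section 5.3 describes the interview as meant to reveal possible related events, section 7.2.2 confines its adverse event item to insertion and tools, and 5.3 expects insertion-related events mostly in the first days. On this view the question fits its purpose.

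Much of this stands. A reader might infer that events are undercounted by rule. The documents do not support that: the rule is to record everything, and the risk is under-elicitation, mainly of unrecognised non-serious events after the 1-week visit. The reply does not remove that risk. A duty to document does not prompt a patient to speak, and a filter applied by the patient can also hide events that the investigator would have graded as possibly related.

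A reader might also infer that patients who cannot be reached leave follow-up early. They do not. Section 8.3.5 sets termination, "when no interview was possible - the date of the CardioReport", at the report behind the 1-month data, and 9.5 uses the recording closest to day 30. Section 9.8 asks for all efforts to reach the patient "to assure that no adverse events will remain unnoticed". Such patients lack an interview, but they are not released early.

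On the exit rule, it is fair that 8.3.4.1 governs exclusion by investigator decision, which is a different case, and that 8.3.4.2 requires existing events to end first. The aim stated in 8.3.4.1 is nevertheless complete reporting over the whole study, and 8.3.4.2 sets no time that would secure it.

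**Conclusion.** Two points hold. The 1-month question in 9.5 is narrower than the recording rule it serves and moves the first causality judgement from the investigator to the patient. Section 8.3.4.2 sets no minimum adverse event follow-up after failed insertion or explantation, so later-onset events in those patients can be missed.

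The likely direction is too few events, but the amount cannot be computed from the protocol. It would be tempting to say that the study's ability to detect unforeseen risks collapses. At the stated 15% rate that is not shown: even an assumed 50% capture leaves a 97.0% chance of seeing at least one event. A larger loss appears only if the rate is set near 6.4%, which the protocol does not state, or if capture is assumed below about 43%. Nor can the expected drop-out of under 10% be read as a count of missed calls. The exit gap concerns about 0.5 of 45 patients from failed insertions, assuming the predecessor's failure rate, plus any explants within one month.

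The case for acting rests on the internal mismatch, the first-in-man setting and the very low cost, not on a demonstrated bias.

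**What to change.** - **Section 9.5:** replace the restricted question with an open, non-leading one about any new symptom, illness, medical contact or change at the wound since the last contact. State that the investigator then grades relatedness under 18.2.1. Use the same wording on the 1-month source data sheet.
- **Section 8.3.4.2:** state that, unless consent is withdrawn, adverse event data for patients with failed insertion or explantation are collected up to and including the same 1-month telephone contact. This brings the section into line with 8.3.4.1 and 5.3.

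The cost is one reworded question, a telephone call for very few patients and somewhat more unrelated events to record and grade. No extra clinic visit or device measurement is needed. Reported event counts may rise slightly.
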